9. STATISTICAL CONSIDERATIONS

9.1 General Design Issues

This is a randomized open-label waiting list controlled study of TARA training in 100 boys and girls aged 14-18 years. They will be individually randomized to 12 weeks of group TARA training sessions (50 to TARA training and 50 to waitlist control). The randomization is open label because there was concern that it was not possible to develop a sham training which would motivate participation and yet have no effects on the desired outcomes.

This study is designed to demonstrate that the TARA training will increase putamen connectivity (primary outcome) and decrease emotional problems on the SDQ questionnaire (secondary outcome).

Primary Hypothesis: Putamen structural node strength (primary outcome) will increase in the training group compared to controls.

Secondary Hypothesis: There will be a significant decrease in emotional problems measured with the Strengths and Difficulties Questionnaire (SDQ) (secondary outcome) in the training group compared to controls.

In our recent published study (Yuan et al., 2019), we demonstrated that diffusion MRI connectome methods can provide reliable and precise network measures, including the node strength, in adolescents.

The SDQ was selected because it is widely used in adolescents to measure internalizing problems and has good psychometric properties (Goodman, 2001).

For more details see section 10.3.3 Metrics.

9.2. Sample Size and Randomization

The study is powered for medium-large effect size of the meditation training on the putamen node strength. With type I error of 0.05, type II error of 0.2 (power of 80%), two-sided effect size of a Cohen's D of 0.6, the required sample size is N=45 subjects who will be studied before and after the TARA training. Given the length of the study (three months), the required commitment to participation in the training, and based on our experience, we assume an attrition rate of 10%; therefore, the target sample size is 50 subjects per group. Our primary analysis will be a general linear model of putamen node strength at week 12 with terms for baseline node strength, treatment assignment and participant sex. The primary analysis will be intent to treat and will include all randomized participants regardless of treatment receipt or protocol violations.

The only clustering in the trial will be the group delivery of the TARA intervention. We anticipate 4 TARA classes of 10-15 participants. We expect the intraclass correlation to be negligible for the following reasons: a) the TARA instructors are trained in standard procedures, b) we expect formidable individual level variation. We therefore did not include cluster assignment in the sample size calculation. We are going to test this assumption in a sensitivity analysis which extended the primary analysis by inclusion of treatment by TARA class interaction.

To standardize TARA delivery, we have included facilitator training and created a very detailed TARA manual (please see Appendix).

Treatment Assignment Procedures

We will use computer-generated randomization with variable blocks sizes of 4, 6 and 8. Individuals will be randomized with no stratification or restricted except the permuted blocks. We will permute 8 blocks of size 8, 2 blocks of size 6, and 4 blocks of size 4. The treatment assignments will be 1:1 within each block and assignments within a block will be permuted. The only masking will be in the administration of questionnaires and in the interpretation of putamen node strength.

The rationale for the use of randomization is to minimize potential biases.

The study is open label to participants, and thus there is no need for unblinding or unblinding procedures.

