1. STUDY OBJECTIVES

1.1 Primary Objective

The **primary objective** will be to study changes in putamen structural connectivity in healthy teens with meditation training. **Hypothesis**: Putamen structural node strength will increase in the training group compared to controls.

R61 Go/No-Go Criteria. Detect an effect size (a threshold of Cohen's d > 0.20) in changes of the primary mechanistic outcome (**Putamen structural node strength**) by the described meditation training in 100 healthy adolescents that are 14-18 years old and retain at least 80% of randomized participants for primary outcome measurement at the end of the study regardless of adherence to the intervention.

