3. STUDY DESIGN

The present research study design will utilize an individually randomized group treatment, open-label, waitlist-controlled clinical trial to test the efficacy and safety of our innovative mindfulness meditation intervention (Training for Awareness Resilience and Action [TARA]) on the primary outcome (Putamen structural node strength) and secondary outcome (emotional problems measured with the Strengths and Difficulties Questionnaire [SDQ]) in healthy adolescents between the ages of 14 to 18 years old.

The specific unit of assignment and unit of observation are the individual study participants.

[figure not shown]
Primary outcome: Putamen structural node strength

Secondary outcome: Emotional problems measured with the Strengths and Difficulties Questionnaire (SDQ)

The study population are 100 healthy adolescents that are 14-18 years old, who are randomly assigned to the intervention or waitlist control group (50 assigned to intervention, 50 assigned to waitlist control who will later receive the intervention).

The entire study will take place at the University of California, San Francisco (UCSF). More specifically, all of the MRI scans will take place at the UCSF Mission Bay campus. All of the TARA group interventions and subject interviews will take place remotely over Zoom.

The approximate duration of subject enrollment period for the entire trial will be 21 months (please see below, R61 Phase Timeline). We plan to run 5 intervention groups and 5 waitlist control groups. The intervention duration is 1.5 hours per week for 12 weeks, and MRI scanning and clinical assessments will be performed within 2 weeks (maximum 4 weeks) before and after the 12-week intervention. Thus, each individual participant who is randomly assigned to the intervention will be followed for a total duration of up to 20 weeks (12 weeks of intervention plus up to 4 weeks before the start of the intervention plus up to 4 weeks after the end of the intervention). The individual participants who are randomly assigned to the waitlist control will be similarly followed for approximately 20 weeks.

Intervention: 12-week group meditation training, Training for Awareness, Resilience, and Action (TARA).

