5. STUDY INTERVENTIONS

5.1 Interventions, Administration, and Duration

The TARA intervention is delivered in a semi-manualized form in 12 consecutive, weekly 1.5hour sessions by two facilitators (who are trained by [name]). In case of a remote delivery of the intervention, a group size of 8-10 participants allows for a good overview of everyone in the group. Participants will be instructed by the TARA facilitators how to best create a quiet, temperature-controlled, comfortable practice space in their home, and how to best use Zoom and camera on their device. Each participant will receive from us props for their practice (a yoga mat, a meditation pillow, an eye pillow, etc.). Daily home practice of TARA skills will be encouraged and audio recordings with guided meditations will be provided. The outline of the **TARA intervention** is as follows (for details, see *[name] Henje et al.*, 2014): *Module 1*: focuses on the ability to create a calm and safe inner state through breathing, yoga-based movement and guided "body-scan" meditations. A brief psycho-educational module on the psychophysiology of stress and respiration is provided. *Module 2*: includes attention training first targeting external stimuli, followed by sensory stimuli and interoceptive awareness. Psycho-education is provided on an adapted neuroscience model and the importance of sleep and healthy eating for emotional health. Module 3: focuses on recognizing, labeling, and communicating emotions. By aiding participants in identifying their emotions and applying skills from modules 1 and 2, the core skills are applied in social interaction. In *Module 4* a more cognitively based behavioral activation approach is introduced, including understanding of social triggers of negative emotions and one's own experiential avoidance strategies and how they may impede obtaining desired life goals. A parallel focus on defining personal core values and linking them to behavior activation is a thread throughout the intervention that serves as a motivational force to increase sustainability and future engagement in salutogenic activity. The meditative practices are continued in all modules.

The attached **TARA Manual** provides extensive details on the content of each TARA session (please see Appendix).

The TARA sessions will take place remotely over Zoom.

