9.6 Data Analyses

Primary Outcome. To attain the primary objective, we will test the hypothesis that an increase in the node strength of the putamen (dependent variable) will be observed in the training group compared to the controls. This hypothesis will be tested using an analysis of covariance (ANCOVA) accounting for sex and fit by maximum likelihood. Stata (College Station, TX) will be used to perform data analyses. The use of maximum likelihood mitigates susceptibility to missing data. Examination of variable distribution and outlier identification will be performed. We will additionally explore age, pubertal status (as determined by the Tanner stage self-report form (Tanner et al., 1962)), and pre-training associations with the changes through an examination of interaction. Potential pre-/post-training differences in movement during MRI will be accounted for by assessing the number of rejected diffusion directions. Sex as a biological variable: In all analyses described, sex will be included as a factor, we will also test for a randomized arm by sex interaction.

The only clustering in the trial will be the group delivery of the TARA intervention. We anticipate 4 intervention arm clusters of 10-15 participants. We expect the intraclass correlation to be negligible for the following reasons: a) the TARA instructors are trained in standard procedures, b) we expect formidable individual level variation. We are going to test this assumption in a sensitivity analysis which extended the primary analysis by inclusion of treatment by TARA class interaction. We are going to test this assumption in a sensitivity analysis which extended the

primary analysis by inclusion of treatment by TARA class interaction.

To standardize TARA delivery, we have included facilitator training and created a very detailed TARA manual (please see Appendix).

In addition, we will examine relationship between changes in node strength of the putamen and adherence to sessions, proportion of sessions attended, by performing a Spearman rank correlation of TARA adherence (by percentage of sessions attended) and change in node strength. We will use ANCOVA analysis with a treatment by attendance interaction to estimate the putamen node strength which would be achieved with full attendance in all training session.

Secondary Outcome.

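### The sample size and primary model assume no correlation within TARA classes, and the planned treatment-by-class interaction can neither confirm that nor correct the treatment standard error

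*Combined protocol and SAP*

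**What the plan says.** Section 3 describes an individually randomized group treatment design. Section 9.2 recognises what follows from it: "The only clustering in the trial will be the group delivery of the TARA intervention". It expects the ICC to be negligible because instructors are trained to a standard and individual variation is large, but gives no value or pilot estimate. It then states: "We therefore did not include cluster assignment in the sample size calculation".

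The primary analysis in Section 9.2 is "a general linear model of putamen node strength at week 12 with terms for baseline node strength, treatment assignment and participant sex". Section 9.6 calls it an ANCOVA fitted by maximum likelihood. Neither section has a class term in that model. The one planned check, stated in both sections, is: "We are going to test this assumption in a sensitivity analysis which extended the primary analysis by inclusion of treatment by TARA class interaction".

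The class numbers differ between sections:

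- Section 9.6 (and Section 9.2 in similar words): "We anticipate 4 intervention arm clusters of 10-15 participants".
- Section 3: "We plan to run 5 intervention groups and 5 waitlist control groups".
- Section 5.1, on remote delivery: "a group size of 8-10 participants allows for a good overview of everyone in the group".

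**The concern.** If participants in the same class resemble each other at week 12, the TARA mean is less precise than the primary model assumes. The p-value is then too small and the confidence interval too narrow. The stated 5% error and 80% power hold only if the ICC is close to zero, so the plan depends on its check of that assumption.

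The check appears unable to do this work, for two reasons. With four or five classes, a non-significant class test says very little about the ICC. And fixed class terms take between-class variation out of the error instead of adding it to the standard error of the treatment effect. A reader could therefore see the check passed and trust a primary p-value that it does not protect.

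**Working it through.** **Inputs from Section 9.2.** Two-sided alpha 0.05, power 80%, d = 0.6, 45 analysed and 50 randomised per arm, 1:1 allocation.

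**Assumptions.** The documents give neither an ICC nor a baseline correlation. ICC is taken as 0, 0.01, 0.05 and 0.10. The base case has no baseline adjustment, as in the plan's own calculation.

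**1. The plan's figure.** The two-sample t-test with d = 0.6 has power 0.795 at 44 per arm and 0.804 at 45, and 45/0.9 = 50. The stated size is reproduced, but only with independent observations.

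**2. What the interaction can estimate.** Take 50 waitlist participants with no class. An intercept, treatment, class indicators and their interactions give 10 columns of rank 5 with 4 classes, and 12 columns of rank 6 with 5 classes. The interaction is aliased with class. After the redundant columns are dropped the model fits, and what remains is a test of differences among TARA classes on 3 or 4 degrees of freedom.

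**3. Effect on the primary test.** With k classes of m = 45/k, the variance of the arm difference is inflated by f = 1 + (m − 1) × ICC/2, because only one arm is clustered. For k = 4, m = 11.25 and ICC 0.05, f = 1 + 10.25 × 0.05/2 = 1.256. Also z = 0.6 × √(45/2) = 2.846.

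- Type I error of the planned test = 2 × [1 − Φ(1.96/√f)]
- Power at a true 5% level = 1 − Φ(1.96 − z/√f)

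| | ICC 0 | 0.01 | 0.05 | 0.10 |
|---|---|---|---|---|
| f, 4 classes | 1.000 | 1.051 | 1.256 | 1.513 |
| Type I error, 4 classes | 5.0% | 5.6% | 8.0% | 11.1% |
| True-5% power, 4 classes | 81% | 79% | 72% | 64% |
| Type I error, 5 classes | 5.0% | 5.5% | 7.4% | 9.8% |
| True-5% power, 5 classes | 81% | 80% | 74% | 67% |

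The 81% is the normal approximation; the t-test gives 80%. Simulation of the 4-class case (40,000 trials per cell) gave true-5% power of 80, 78, 71 and 62%.

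**4. Baseline adjustment.** Assume a baseline correlation of 0.3 to 0.5, unchanged class variance and 4 classes. At ICC 0.05 the type I error is 8.2–8.7% and true-5% power 74–80%. At ICC 0.10 they are 12.0–13.2% and 65–70%. Adjustment recovers some power but does not restore the error rate.

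**5. Power of the class test.** The F statistic on (k − 1, 45 − k) degrees of freedom is scaled by 1 + m × ICC/(1 − ICC).

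| | ICC 0.05 | ICC 0.10 | ICC needed for 80% power |
|---|---|---|---|
| 4 classes | 17% | 30% | about 0.40 |
| 5 classes | 15% | 28–29% | about 0.37 |

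Even with an observed F of 1 (estimated ICC of zero), the upper 95% limit for the ICC is 0.54 with 4 classes and 0.45 with 5.

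**6. Does passing the test protect the primary result?** In simulated 4-class trials with a non-significant class test, the primary type I error was 8.2% at ICC 0.05 (7.9–8.6% across runs) and 11.4% at ICC 0.10.

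**7. Do fixed class terms correct the treatment test?** No. With 4 classes of 11 (8,000 trials per cell), type I error with the class terms was 7.9% at ICC 0.05 and 11.8% at ICC 0.10, against 7.5% and 11.2% without them.

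**8. Go/no-go rule.** Section 1.1 sets "Detect an effect size (a threshold of Cohen's d > 0.20) in changes of the primary mechanistic outcome". With no true effect, the chance that observed d exceeds 0.20 is 1 − Φ(0.2/√(2f/45)). With 4 classes this is 17.1, 17.7, 19.9 and 22.0% at ICC 0, 0.01, 0.05 and 0.10.

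**9. Class numbers.** Fifty participants in 4 classes is 12.5 each, outside 8–10. Four classes of 8–10 hold 32 to 40 people, fewer than 50. Five classes of 10 would fit Sections 3 and 5.1 but not Sections 9.2 and 9.6.

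**The case against.** - **The interaction might be meant as random.** A random class effect multiplied by the treatment indicator would be the class term of a partially nested model, and it would enter the standard error. But the text adds an interaction to a general linear model and names no random effect; maximum likelihood does not imply one. If this was meant, it has to be written.
- **The waitlist groups could be the classes.** Section 3 mentions five. The interaction could then be estimated, but as a fixed term it would still leave the standard error uncorrected. The coding is not stated.
- **The clustering is disclosed and the ICC may be tiny.** Both points are fair. At ICC 0.01 the error is 5.6% and power 79%, which is of no consequence. The sample size is unsupported; it is not shown to be too small. What stands is that the plan cannot tell which case holds.
- **This is a preliminary study with a go/no-go rule.** The rule moves only from 17% to 20% at ICC 0.05, and the treatment estimate is not biased. But Sections 9.2 and 9.6 also plan a hypothesis test at the 5% level, and that test is affected.
- **The remedy is weak with four classes too.** In simulation of a balanced equivalent of the mixed model at ICC 0.05, class variance was estimated as zero in 40% of trials, and type I error in those trials was again 8.2%. Overall, however, the error was 4.4%, with power 59% (70% at ICC 0). No model can establish a negligible ICC from four classes. The mixed model does control the error on average, which the planned check does not.

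**Conclusion.** The concern holds and should be fixed. That the interaction is aliased with class when class exists only in the TARA arm, that fixed class terms leave the treatment standard error uncorrected, and that the class numbers conflict do not depend on the size of the ICC. The size of the harm does: with 4 classes it is trivial at ICC 0.01, and at 0.05 to 0.10 the primary type I error is roughly 8% to 11% and true-5% power 72% to 64%, before baseline adjustment. These ICCs are assumptions, not estimates for this trial. The damage is confined to the p-value, the confidence interval and the power claim.

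**What to change.** In Sections 9.2 and 9.6:

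1. Replace the treatment-by-class interaction with a partially nested mixed model as the named sensitivity analysis. Use the primary model's covariates, a random class effect in the TARA arm only, waitlist participants as singletons, arm-specific residual variances, REML, and Satterthwaite or Kenward-Roger degrees of freedom.
2. Report the ICC with its confidence interval, and say that a non-significant class test will not be taken as evidence of a negligible ICC.
3. State that the 80% power assumes ICC 0, and add power for ICC 0.01 to 0.10.
4. Use one number and size of classes in Sections 3, 5.1, 9.2 and 9.6.

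Whether this model should be primary with only four or five classes is for the sponsor to decide.

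**Cost.** SAP text and a few lines of Stata, with no extra participants. The model pays in precision. Approximated by a class-mean Satterthwaite test with 4 classes and no baseline adjustment, power at d = 0.6 is 71–73% at ICC 0, 60–61% at 0.05 and 52% at 0.10, with type I error 3.6–6.1%. The median half-width of the 95% interval goes from 0.42 SD under the planned model to 0.43–0.44 SD at ICC 0 and 0.49 SD at ICC 0.05.

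Restoring 80% power at a true 5% level by adding classes of the same size would take 45 × f, about 54–57 analysed per arm at ICC 0.05 and 63–68 at ICC 0.10 (53–55 and 62–66 if the normal-approximation base of 44 is used). That is given for scale and is not requested.

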9.3 Definition of Populations

The intent to treat population will consist of all participants randomized into the trial regardless of treatment receipt or protocol violations.

The per protocol population will consist of all participants in the intervention group who participate in at least 75% of TARA training session plus all those in the wait list control group.

9.4 Interim Analyses and Stopping Rules

This trial will not have any interim analyses. It is itself a preliminary study which will lead to a decision about whether a follow-on study will be conducted in depressed adolescent volunteers.

Safety findings that will trigger a safety review: If 15% of the enrolled study participants experience a Grade 2 (moderate) or Grade 3 (severe) adverse event (AE) related to the TARA study intervention, then a safety review will occur.

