The current research study design will utilize an individually randomized group treatment, open-label, waitlist-controlled clinical trial to test the efficacy and safety of our innovative mindfulness meditation intervention (Training for Awareness Resilience and Action [TARA]) on the primary outcome (Putamen structural node strength) and secondary outcome (emotional problems measured with the Strengths and Difficulties Questionnaire [SDQ]) in healthy adolescents between the ages of 14 to 18 years old.

Please see below, Section 6.1 (Schedule of Evaluations), for detailed schedule and type of evaluations to be performed during the study.

R61 Overview Diagram of Study Design:

Interventions and Duration

The current study will specifically compare 12-week group meditation training intervention (TARA) with a waitlist control group. Each adolescent participant will be on study for the period of 12-weeks.

Sample Size and Population

The target population for the current study will be 100 healthy female and male adolescents that are between the ages of 14 to 18 years old who are randomly assigned to the 12-week meditation training intervention (TARA) or waitlist control group (50 healthy female and male adolescents between the ages of 14-18 years will be assigned to the 12-week meditation training intervention, and 50 healthy female and male adolescents between the ages of 14-18 years will be assigned to the waitlist control group). Randomization will not be stratified.

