6.2.2 Enrollment, Baseline, and/or Randomization

Enrollment

The current study will utilize a single informed signed consent form that describes both screening and study procedures. Thus, in the current study, the enrollment date is defined as the date all of the screening criteria are met and the individual agrees to participate which is also the same date as the randomization date (i.e., Visit 1 [Day 0]). Please see above, Section 6.1, Schedule of Evaluations Table. The enrollment date will be recorded on a case report form (please see included Randomization and Enrollment form) along with the allowable window between screening and randomization (please see above section, "Screening", for the precise allowable time window between screening and randomization).

Baseline Assessments

The following baseline evaluations will occur on Visit 1 (Day 0) of the study:

MRI brain scan. An MRI brain scan will be acquired at baseline to compare

- against the final MRI brain scan that will be obtained at the final visit (Visit 14).
- Strengths and Difficulties Questionnaire (SDQ). Emotional problems will be assessed in all participants at baseline using the SDQ in order to compare with the SDQ that will be collected at the final visit (Visit 14).

Randomization

Computer-generated randomization will precede intervention administration in the current randomization study. The time window for randomization relative to completion of screening and baseline will be 24 hours (i.e., randomization as well as completion of screening and baseline will all occur the same day). The time window for initiation of study intervention relative to randomization will be 4 (four) weeks.

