7.3 Adverse Events and Serious Adverse Events

In the present study, an adverse event and serious adverse event will be defined as follows:

An adverse event (AE) will be defined as any unfavorable and unintended diagnosis, symptom, sign (including an abnormal laboratory finding), syndrome or disease which either occurs during the study, having been absent at baseline, or if present at baseline, appears to worsen. Adverse events will be recorded regardless of their relationship to the study intervention.

A **serious adverse event (SAE)** will be defined as any untoward medical occurrence that results in death, is life threatening, requires inpatient hospitalization or prolongation of existing hospitalization, results in persistent or significant disability/incapacity, or is a congenital anomaly.

Since we do not anticipate any laboratory value changes due to the TARA study intervention, no laboratory values will be collected as part of the current protocol; thus, no laboratory values will be collected to assess safety.

Solicited adverse events will be captured in the following manner: (1) the Child Outcome Rating Scale (CORS) including the following question: "Has there been any significant unfavorable change in your mental or physical health since last class?" will be administered at every TARA session (please see Appendix. Not a source document.); (2) if the participant answers "no" to this question on the CORS, then no additional information will be requested; (3) if the participant answers "yes" to this question on the CORS and the reported event meets the definition of an adverse event given above, then the research assistant or another study staff member will ask the participant for additional details regarding the participant's answer to the CORS question and this information will be recorded in the Adverse Event form within 24 hours of the TARA study intervention session.

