7.5 Followup for Adverse Events

The PIs will record all reportable events with start dates occurring any time after informed consent is obtained until 7 days (for non-serious AEs) or 30 days (for SAEs) after the last day of study participation. At each study visit, the investigator will inquire about the occurrence of AE/SAEs since the last visit. Events will be followed for outcome information until resolution or stabilization. In the cases of adolescents with severe depression or adolescents expressing passive suicidal ideation (i.e., the adolescent expresses some potential thoughts of self-harm, but there is no intent or plan to harm herself/himself), study participants with commercial or private health insurance plans will be referred to the UCSF Langley Porter Psychiatric Institute where [name] (co-PI) sees patients, and study participants without commercial or private insurance will be referred to the UCSF Zuckerberg San Francisco General Hospital which cares for all patients regardless of their ability to pay. Participants expressing imminent suicidal ideation will be placed on an involuntary 5150 72-hour hold for danger to self by [name]. [name] is a double board certified adult as well as child and adolescent psychiatrist who sees patients at UCSF, and he is legally authorized to place an involuntary 5150 72-hour hold on the adolescent for danger to self (i.e., suicidal ideation) in order to hospitalize the adolescent if needed. The UCSF Emergency Room (ER) is located immediately adjacent to the UCSF Langley Porter Psychiatric Institute where [name] personal clinical office and research lab are located. Following the established written protocols that are currently in place for any adolescent who expresses imminent suicidal ideation, [name] would evaluate and place an involuntary 5150 72-hour hold for danger to self on the suicidal adolescent. [name] would then contact the UCSF Langley Porter Psychiatric Institute security who are present in the building throughout the entire day and evening to help escort the suicidal adolescent to the UCSF ER. The ER physician in consultation with the on call child and adolescent psychiatrist would then evaluate the patient in the ER and decide whether to hospitalize the patient for the adolescent's safety and well-being.

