8. INTERVENTION DISCONTINUATION

Participants who have met inclusion/exclusion criteria and been enrolled into the study may be discontinued if they no longer meet the study's inclusion and exclusion criteria (e.g., if the patient has started participation in another mindfulness-based intervention such as mindfulness-based stress reduction after they have enrolled into the TARA study intervention). The PIs (Drs. [name] and [name]) will determine when criteria are met (i.e., the participant no longer meets the study's stated inclusion and exclusion criteria) for discontinuing intervention for a participant.

Possible reasons for discontinuation of the study intervention include closure by the institute (i.e., UCSF) due to significant concerns over the continued safety of the participants such as the occurrence of a natural disaster (e.g., earthquake) that renders the buildings at UCSF where the TARA study intervention is being delivered unsafe due to structural building damage arising from the earthquake.

If the TARA study intervention is discontinued for a participant (i.e., the participant no longer meets the original study entrance inclusion and exclusion criteria), the participant will be followed for one additional visit in order to allow for all of the final visit (Visit 14) assessments to be performed. Once the final visit (Visit 14) assessments are completed, the participant will no longer continue to be followed except to follow any AEs or SAEs as stated above in Section 7.4 (i.e., until 7 days [for non-serious AEs] or 30 days [for SAEs] after the last day of study participation).

A participant who has been enrolled into the study may temporary discontinue treatment if the reason for discontinuation (e.g., cold) does not preclude the participant from successfully completing the remaining study visits without missing greater than 25 percent of the 12 total TARA intervention sessions (i.e., the participant must be able to attend and complete at least 75 percent of the 12 total TARA intervention sessions) within the timeframe specified in this study (please see above, Section 6.1, Schedule of Evaluations).

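### Read literally, the Section 9.4 safety-review trigger divides TARA-related adverse events by both arms, so unless later waitlist TARA is counted it needs 15 of 50 TARA-arm participants (30%), against 8 of 50 (16%) on a TARA-arm denominator

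*Combined protocol and SAP*

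**What the plan says.** Section 9.4 sets the only numerical condition for starting a review of safety, which begins "If 15% of the enrolled study participants experience a Grade 2 (moderate) or Grade 3 (severe) adverse event (AE) related to the TARA". Section 6.2.2 defines the enrolment date as the date when screening criteria are met and "the individual agrees to participate which is also the same date as the randomization date". Enrolment therefore covers both arms, planned at 50 and 50 (Sections 3 and 9.1). Section 8 uses the word more loosely, describing a patient who starts another mindfulness programme "after they have enrolled into the TARA study intervention".

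The control arm is not permanently unexposed. Section 3 describes "50 assigned to waitlist control who will later receive the intervention". On whether adverse events during that later course are recorded, the documents point two ways:

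- Against: the Précis (Interventions and Duration) says "Each adolescent participant will be on study for the period of 12-weeks", Section 3 follows waitlist participants for about 20 weeks, the Section 6.1 schedule ends at Visit 14, and Section 7.5 records events "until 7 days (for non-serious AEs) or 30 days (for SAEs) after the last day of study participation".
- For: Section 7.3 says the adverse event question "will be administered at every TARA session", with no restriction by arm.

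Sections 7.1 and 9.5.2 use the same 15% level, grades and attribution as the criterion for showing that TARA is safe. Their denominator is simply the participants, without naming an arm.

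**The concern.** The numerator of the 9.4 percentage can properly come only from adolescents who have received TARA. The literal denominator also includes a waitlist arm of equal size that has not received it. A rule that looks like a 15% limit then acts at about twice that proportion among those exposed. The participants are healthy 14- to 18-year-olds, and Section 9.4 says the trial will inform whether a follow-on study is run in depressed adolescents. A review that starts later than the stated percentage suggests is therefore worth correcting, even for an intervention described as very minimal risk.

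**Working it through.** **Inputs.** Trigger level 15% (Section 9.4). Enrolled 100, allocated 50 TARA and 50 waitlist (Sections 3 and 9.1). The plan gives no participant count for the trigger, so there is none to reproduce. The arm size behind the denominators does reproduce: a two-sample t-test with d = 0.6, two-sided alpha 0.05 and 80% power needs 44.6, so 45 per arm, and 45 / 0.90 = 50 (Section 9.2).

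**Count needed at full enrolment.** The count is 0.15 × denominator, rounded up.

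- All enrolled: 0.15 × 100 = 15. If only the TARA arm has been exposed, 15/50 = 30%.
- TARA arm: 0.15 × 50 = 7.5, so 8. 8/50 = 16% (7/50 = 14% falls short).
- All 100 exposed and later waitlist events counted: 15/100 = 15%, and the discrepancy is gone.

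**Does the result depend on the size of the trial?** With equal arms of n, the literal rule needs 0.15 × 2n / n = 30% of the TARA arm before rounding. The block sizes listed in Sections 3 and 9.2 give 8×8 + 2×6 + 4×4 = 92 rather than 100. With 46 per arm, 0.15 × 92 = 13.8 gives 14/46 (30.4%), and 0.15 × 46 = 6.9 gives 7/46 (15.2%). The factor of about two remains.

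**Chance of a review, one look at full enrolment.** X is Binomial(50, p), where p is the true proportion of TARA participants with a related Grade 2 or 3 event. The documents give no value for p, so these rates are assumptions.

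| True rate p | As written, P(X ≥ 15) | TARA-arm denominator, P(X ≥ 8) |
|---|---|---|
| 5% | 0.0000 | 0.0032 |
| 10% | 0.0001 | 0.1221 |
| 15% | 0.0053 | 0.4812 |
| 20% | 0.0607 | 0.8096 |
| 25% | 0.2519 | 0.9547 |

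If all 100 were exposed and counted, X would be Binomial(100, p), and P(X ≥ 15) would be 0.5428, 0.9196 and 0.9946 at 15%, 20% and 25%.

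**The case against.** The strongest reply is that this is loose wording and the intent is clear. The criterion appears three times with the same level, grades and attribution, and Section 8 uses enrolment for people receiving TARA, so 9.4 may simply be the monitoring counterpart of 7.1. That may well be what was meant. But Section 6.2.2 gives enrolment a definite meaning, and no visible text limits the 9.4 denominator to those exposed. Section 7.6 refers to a data and safety monitoring plan that is not among the documents and might define it.

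A second reply is that waitlist participants do receive TARA later. If their events count, the rule acts at 15% once all 100 are exposed. This condition is real and the conclusion carries it. The stated time on study, the schedule and the recording window make counting the less likely reading.

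A third is that oversight does not rest on this trigger, and that stands. The investigators decide on action after each adverse event (Section 7.2) and go through the forms weekly (Section 7.3). The Independent Monitors receive unblinded case-by-case reports (Section 6.2.3) and semi-annual adverse event rates (Section 7.4, Table A). The final analysis compares adverse events by arm (Section 9.6), so the denominator in 9.4 cannot dilute it. These arrangements limit the consequence but do not change what 9.4 states.

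A smaller point is that the investigator who attributes events is meant to be blinded to arm (Sections 5.2 and 6.2.3), so a waitlist event could be attributed to TARA. That would be a misattribution, and it would lower the TARA-arm count needed.

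**Conclusion.** The point holds, conditionally, and is minor. Read literally, and with later waitlist events not counted, the trigger needs 15 of 50 TARA-arm participants (30%), against 8 of 50 (16%) with a TARA-arm denominator. The counts follow from the plan's own figures. The review probabilities rest on assumed event rates and a single look at full enrolment.

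Three stronger inferences are not supported:

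- A reader might conclude that the plan deliberately sets a 30% limit. The 30% depends on the literal denominator and on leaving out later waitlist TARA, and the documents settle neither beyond doubt.
- A reader might extend the fault to the safety criterion in Sections 7.1 and 9.5.2. There the participants probably already means TARA recipients: 9.5.2 specifies randomized participants when it defines retention, yet uses participants alone for tolerability, which is rated after TARA sessions. Those sections need matching wording only.
- A reader might conclude that harm would go unnoticed. The trigger starts a review and stops nothing, and the other reviews continue regardless.

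**What to change.** In Section 9.4, take the percentage over participants exposed to TARA. That means the TARA arm, plus waitlist participants who later receive TARA only if their adverse events are collected, in which case they enter both numerator and denominator. State which of these applies, and use the same denominator wording in Sections 7.1 and 9.5.2. The 15% level, the grade range and the timing of looks remain for the sponsor and monitors. Section 9.4 does not say when the percentage is evaluated, and that is a separate choice.

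The cost is one sentence in 9.4 and a wording alignment in two other sections. No new data collection is needed; collecting adverse events during later waitlist TARA would be a separate procedural decision. The downside is more reviews when the event rate is low: at an assumed true rate of 10% and one look, 12% against under 0.1% as written, and at 5%, 0.3% against under 0.1%. More frequent looks would raise these chances, which is a further reason to leave timing to the sponsor and monitors.
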